12.5.4 Overall Response Assessment

Table 4: Overall Response Evaluation for Neuroblastoma Patients and MIBG Positive Disease Only

If patients are enrolled without disease measurable by CT/MRI, any new or newly identified lesion by CT/MRI that occurs during therapy would be considered progressive disease.

MIBG	CT/MRI	Bone Scan	Bone Marrow	Catechol	Overall
PD	Any	Any	Any	Any	PD
Any	New Lesion	Any	Any	Any	PD
Any	Any	PD	Any	Any	PD
Any	Any	Any	PD	Any	PD
SD	No New Lesion	Non-PD	Non-PD	Any	SD
PR	No New Lesion	Non-PD	Non-PD	Any	PR
CR	No New Lesion	Non-PD	Non-PD	Elevated	PR
CR	No New Lesion	CR	CR	Normal	CR

12.5.5 Overall Best Response Assessment

Each patient will be classified according to his “best response” for the purposes of analysis of treatment effect. Best response is determined from the sequence of the overall response assessments as described in [Section 12.9](#).

12.6 **Response Criteria for Neuroblastoma Patients with Bone Marrow Involvement**

12.6.1 Bone Marrow Involvement

Note: patients with bone marrow as the ONLY site of disease are not eligible for this study. Response criteria in this section are intended to be used when assessing marrow involvement as a component of overall response.

Histologic analysis at the local institution of marrow tumor cell involvement is **required** for patients with a history of marrow involvement. Marrow aspirate and biopsy should be evaluated at baseline and every 2 cycles thereafter. Note: If progressive disease is documented by RECIST criteria using tumor measurements or by MIBG scan, then a repeat BM is not needed to confirm PD.

Complete Response: No tumor cells detectable by routine morphology on 2 consecutive bilateral bone marrow aspirates and biopsies performed at least 21 days apart. Normalization of urinary catecholamines or other tumor markers if elevated at study enrollment.

Progressive Disease: In patients who enroll with neuroblastoma in bone marrow by morphology have progressive disease if there is a doubling in the amount of tumor in the marrow AND a minimum of 25% tumor in bone marrow by

morphology. (For example, a patient entering with 5% tumor in marrow by morphology must increase to $\geq 25\%$ tumor to have progressive disease; a patient entering with 30% tumor must increase to $> 60\%$).

In patients who enroll without evidence of neuroblastoma in bone marrow will be defined as progressive disease if tumor is detected in 2 consecutive bone marrow biopsies or aspirations done at least 21 days apart.

Stable Disease:

Persistence of tumor in bone marrow that does not meet the criteria for either complete response or progressive disease.

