Circulating Tumor DNA (ctDNA-optional) ⁹			Cycle 5, Day 1 and (for patients receiving \geq 5 cycles only) at end of Protocol Therapy OR disease progression

[^] Studies may be obtained within 72 hours prior to the start of the subsequent cycle.

- 1 Women of childbearing potential require a negative pregnancy test prior to starting treatment; sexually active patients must use an acceptable method of birth control. Abstinence is an acceptable method of birth control.
- 2 If patients have Grade 4 neutropenia then CBCs should be checked at least every other day until recovery to Grade 3 or until meeting the criteria for dose limiting toxicity.
- 3 If patients develop Grade 3 or higher thrombocytopenia then CBCs should be checked every 3-4 days until recovery per [Section 6.1](#)
- 4 Tumor Disease Evaluation should be obtained on the next consecutive cycle after initial documentation of either a PR or CR. Subsequent scans may restart 2 cycles after the confirmatory scan. If the institutional investigator determines that the patient has progressed based on clinical or laboratory evidence, he/she may opt not to confirm this finding radiographically.

4-A Neurological exam also required for CNS patients

4-B Non- Hodgkin Lymphoma/ Histiocytosis patients are required to have PET scans within 2 weeks prior to start of therapy and should also be followed with PET scans if positive at diagnosis. Refer to [Section 12.8](#)

4-C Patients with neuroblastoma must have both CT/MRI and MIBG scintigraphy prior to enrollment if the patient was enrolled with or has a history of having MIBG avid tumor. Otherwise the patient must have both CT/MRI and bone scan prior to enrollment. For patients with neuroblastoma and measurable disease by CT or MRI, lesions should be measured and followed using the same modality (CT or MRI) in addition to MIBG or bone scan. For patients with neuroblastoma and evaluable disease by MIBG scintigraphy or bone scan, use the same modality (MIBG scintigraphy or bone scan) to image and follow patients; CT/MRI are not required but may be performed as

clinically indicated. Refer to [Section 12.5.4](#) and [Section 12.9](#)

- 5 Bone marrow aspirate and/or biopsy only required in patients suspected of having bone marrow metastasis on the basis of history, symptoms, laboratory evaluation or other clinical data. Should only be performed on patients with known bone marrow involvement at baseline.

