- 6 Bone marrow aspirate and/or biopsy should be performed only when complete response or partial response is identified in target disease or when progression in bone marrow is suspected.
- 7 Medication diary (see [Appendix III](#)) should be reviewed after completion of each treatment cycle and uploaded into RAVE. The medication diary should be collected and reviewed weekly during cycle 1.
8. See [Section 8.4](#) for details of PK studies.
9. With consent two samples will be collected on this protocol (Cycle 5 Day 1; and for patients receiving ≥ 5 cycles, at progression or end of protocol therapy) see [Section 8.5](#) and [Appendix IV](#) for details of the ctDNA studies. Note that a ctDNA sample is scheduled to be obtained on the APEC162SC screening protocol prior to the initiation of treatment on this subprotocol
10. Ophthalmological examinations will be performed by an ophthalmologist at screening and if clinically indicated during treatment.
11. Plain radiographs of at least one tibial growth plate should be obtained in all patients prior to first dose of protocol therapy. In patients with open growth plates, follow-up plain radiographs of the same growth plate(s) should be obtained according to [Section 8.2.1](#).

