		10	mg AM mg PM	
		11	mg AM mg PM	
		12	mg AM mg PM	
		13	mg AM mg PM	
		14	mg AM mg PM	
		15	mg AM mg PM	c
		16	mg AM mg PM	
		17	mg AM mg PM	
		18	mg AM mg PM	
		19	mg AM mg PM	
		20	mg AM mg PM	
		21	mg AM mg PM	
		22	mg AM mg PM	c
		23	mg AM mg PM	
		24	mg AM mg PM	

	25	mg AM	mg PM	
	26	mg AM	mg PM	
	27	mg AM	mg PM	
	28/1	mg AM	mg PM	a-f, g*, i, j*, k*, l*, m*

Following completion of this cycle, the next cycle starts on Day 29 or when the criteria in [Section 5.2](#) are met (whichever occurs later).

See [Section 6.0](#) for Dose Modifications for Toxicities and the COG Member website for Supportive Care Guidelines

* Please refer to [section 8.1](#) for the specific timing of these observations. Studies on Day 28/1 may be obtained within 72 hours prior to the start of the subsequent cycle.

Required Observations in All Subsequent Cycles

a.	History/Physical Exam (including VS)
b.	Ht/Wt/BSA
c.	CBC/differential/platelets- If patients have Grade 4 neutropenia then CBCs should be checked at least every other day until recovery to Grade 3 or until meeting the criteria for dose limiting toxicity. If patients develop Grade 3 or greater thrombocytopenia then CBCs should be checked every 3 to 4 days until recovery per section 6.1 .
d.	Electrolytes including Ca++, PO4, Mg++
e.	Creatinine, ALT, bilirubin
f.	Albumin
g.	Tumor Disease Evaluation – Every other cycle x 3 then q 3 cycles. Tumor Disease Evaluation should be obtained on the next consecutive cycle after initial documentation of either a PR or CR. Subsequent scans may restart 2 cycles after the confirmatory scan. If the institutional investigator determines that the patient has progressed based on clinical or laboratory evidence, he/she may opt not to confirm this finding radiographically
h.	Bone Marrow Aspirate and/or biopsy- Only required in patients suspected of having bone marrow metastasis on the basis of history, symptoms, laboratory evaluation or other clinical data. Should only be performed on patients with known bone marrow involvement at baseline. Bone marrow aspirate and/or biopsy should be performed only when complete response or partial response is identified in target disease or when progression in bone marrow is suspected.
i.	Medication Diary- (see Appendix III) should be reviewed after completion of each treatment cycle and uploaded into RAVE. The medication diary should be collected weekly.

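### For neuroblastoma patients with a marrow history, Section 12.6.1 calls for marrow every 2 cycles while Section 8.1 and Appendix VI allow it only on a trigger, so marrow-only progression is ascertained under two conflicting rules

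*Combined protocol and SAP*

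**What the plan says.** Section 12.6 applies to neuroblastoma. Section 12.6.1 makes local marrow histology a requirement "for patients with a history of marrow involvement" and fixes the timing: "Marrow aspirate and biopsy should be evaluated at baseline and every 2 cycles thereafter". One exception is given: if PD is already shown by RECIST or on MIBG scan, "then a repeat BM is not needed to confirm PD".

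The Section 8.1 table has one entry in the marrow row, at pre-study. Footnote 6 says that marrow tests "should be performed only when complete response or partial response is identified in target disease or when progression in bone marrow is suspected". Footnote 5 adds: "Should only be performed on patients with known bone marrow involvement at baseline". Appendix VI, item h for subsequent cycles, repeats both footnotes. The Day 28/1 list on that map runs from a to g and then i to m, so marrow (h) is on no scheduled day.

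For patients who enroll without marrow disease, Section 12.6.1 defines marrow PD as the case where "tumor is detected in 2 consecutive bone marrow biopsies or aspirations done at least 21 days apart". Marrow CR needs the following: "No tumor cells detectable by routine morphology on 2 consecutive bilateral bone marrow aspirates and biopsies performed at least 21 days apart".

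**The concern.** A rule that fixes marrow tests by the calendar cannot be followed together with one that confines them to named events. Neither Section 8.1 nor item h exempts neuroblastoma, although footnote 4-C of the same table gives neuroblastoma its own imaging rules. Two sites acting in good faith could therefore examine the marrow of similar patients on different plans.

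The endpoint affected is PFS. In Tables 3 and 4, PD in the marrow makes the overall assessment PD whatever the other modalities show. Marrow histology is read locally, and Section 11.7 counts a local progression call as an event even if central review disagrees. Progression also ends protocol therapy (Sections 5.1 and 10.1). If marrow progresses while imaging is stable and nothing raises suspicion, one rule has a scheduled look that can find it and the other has none. The number of marrow procedures a child undergoes depends on the same choice.

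**Working it through.** The plan gives no figure on this point to reproduce, so the check sets the texts side by side and then counts procedures.

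**1. The two rules**

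| | Section 12.6.1 | Section 8.1 footnotes 5–6; Appendix VI item h |
|---|---|---|
| Who | Neuroblastoma with a marrow history | Patients with suspected marrow metastasis (first sentence of footnote 5); patients with known baseline involvement (second sentence) |
| Baseline | Yes | Yes |
| On treatment | Every 2 cycles | Only at CR/PR in target disease or suspected marrow progression |
| Exception | PD already shown by RECIST or MIBG | None stated |

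The baseline test is common to both. The conflict concerns on-treatment tests and who should have them.

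**2. Count over the longest treatment**

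Inputs: a maximum of 26 cycles (Sections 5.1 and 10.1) of 28 days each, and a patient with stable target disease and no suspected marrow progression throughout.

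- Section 12.6.1: 26 / 2 = 13 marrows, after cycles 2, 4, …, 26. Two cycles are 2 × 28 = 56 days.
- Section 8.1 and Appendix VI: no trigger occurs, so 0 marrows.

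For a patient treated for 6 cycles, the same count gives 6 / 2 = 3 against 0.

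**3. Fit with the imaging schedule**

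Imaging is every other cycle three times, then every 3 cycles: after cycles 2, 4, 6, 9, 12, 15, 18, 21 and 24, which is 9 time points. Six coincide with the two-cycle marrow schedule (2, 4, 6, 12, 18, 24). Seven marrow time points have no scheduled imaging (8, 10, 14, 16, 20, 22, 26), and 9 − 6 = 3 imaging time points have no marrow due (9, 15, 21). So even under Section 12.6.1 some overall assessments fall where no marrow is due, and the tables do not say what to enter.

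**4. Where marrow enters the overall response**

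- Table 3 (9 rows): the marrow cell is Any in 3, PD in 1, Non-PD in 4 and CR in 1.
- Table 4 (8 rows): Any in 3, PD in 1, Non-PD in 3 and CR in 1.

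Marrow PD alone is enough for overall PD. SD and PR need only Non-PD. Only overall CR needs marrow CR.

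**5. Effect on the primary endpoint**

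ORR counts CR and PR alike. Footnote 6 triggers a marrow when either is identified, and Section 12.3 asks for a confirmatory scan at the next cycle. A second marrow at that visit would be about 28 days after the first, which exceeds the 21 days required for marrow CR. A missing second marrow would mostly move a patient between CR and PR. The decision rule of at least 3 responses in 20 is untouched: its exact binomial properties are alpha 0.0755 at a 5% response rate and power 0.909 at 25%, in line with the stated 10% and 90%.

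**6. Footnote 5**

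Item h repeats the first sentence of footnote 5: "Only required in patients suspected of having bone marrow metastasis on the basis of history, symptoms, laboratory evaluation or other clinical data". The next sentence limits testing to known baseline involvement. A patient enrolled without marrow disease who later comes under suspicion fits the first sentence and footnote 6 but not the second sentence, and that is the patient for whom Section 12.6.1 writes its two-marrow PD rule.

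**The case against.** The strongest reply is that Section 12.6.1 is the disease-specific rule and so overrides a general schedule. That is a sensible reading, but the protocol does not state it, and the word only in footnote 6 and item h leaves no room for it.

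The objections on scope and size largely stand. The two-cycle rule covers only neuroblastoma with a marrow history. Neuroblastoma is one of 15 named target histologies in Appendix VII, Section 2.1 puts NRAS/PTPN11 mutations at 2.9–3.6% of neuroblastomas, and no count is given. On the other side, patients with known marrow metastases are eligible (Section 4.1.7.1), and a neuroblastoma expansion cohort of 10 could concentrate them.

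Section 8.1 is also not blind to marrow progression. Marrow-only disease is ineligible, so every patient has other disease under scheduled evaluation. The Curie score covers nine osteomedullary sectors, blood counts continue weekly, and suspicion permits a marrow.

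Three stronger readings are tempting and unsupported:

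- A reader might infer that every row of Tables 3 and 4 turns on marrow. It is Any in 3 of 9 and 3 of 8 rows.
- A reader might put the delay in PFS at one imaging interval, 56 to 84 days. An event-driven rule has no interval, so no delay can be derived from the documents.
- A reader might take footnote 5 as a bar on marrow tests in patients without baseline disease. Its first sentence and footnote 6 point the other way, so it is unclear rather than prohibitive.

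**Conclusion.** The conflict is real, is in current text, and should be corrected. For a neuroblastoma patient with a marrow history, stable target disease and no suspected marrow progression, the documents support either 13 or 0 on-treatment marrows over 26 cycles. The consequence is site-dependent detection and dating of marrow-only progression, hence of PFS, and a site-dependent procedure burden.

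The limits are equally clear. PFS is a secondary endpoint estimated by Kaplan-Meier without a test. It would be wrong to conclude that the primary analysis is compromised: the effect on ORR is small and the operating characteristics do not change. That view assumes that target disease in footnote 6 is read to include MIBG-positive disease in patients without measurable lesions. The number of patients affected is unknown and may be few or none. The figure of 13 assumes treatment to the maximum and counts the evaluation after cycle 26. Which schedule is clinically appropriate is not judged here.

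**What to change.** - Reconcile Section 12.6.1, Section 8.1 (marrow row and footnotes 5 and 6) and Appendix VI (item h and the Day 28/1 list) to one marrow schedule and one population. The choice is clinical and belongs to the sponsor.
- State how the marrow column of Tables 3 and 4 is filled at evaluations where no marrow is due.
- Make the two sentences of footnote 5 agree with each other and with the Section 12.6.1 PD rule for patients enrolled without marrow disease.

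The cost is a wording amendment in those places, with no procedure that an existing section does not already require. The practical cost depends on the choice: settling on the two-cycle rule would take a site now following Section 8.1 from 0 to as many as 13 on-treatment marrows for such a patient, while settling on the event-driven rule would add none for a site now following Section 12.6.1.

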12.6.2 Overall Best Response Assessment

Each patient will be classified according to his “best response” for the purposes of analysis of treatment effect. Best response is determined from the sequence of the overall response assessments as described in [Section 12.9](#).

12.7 Response Criteria for Patients with CNS Tumors

12.7.1 Measurable Disease

Any lesion that is at minimum 10 mm in one dimension on standard MRI or CT, for CNS tumors.

12.7.2 Evaluable Disease

Evaluable disease is defined as at least one lesion, with no lesion that can be accurately measured in at least one dimension. Such lesions may be evaluable by nuclear medicine techniques, immunocytochemistry techniques, tumor markers, CSF cytology, or other reliable measures.

12.7.3 Selection of Target and Non-Target Lesions

For most CNS tumors, only one lesion/mass is present and therefore is considered a “target” for measurement/follow up to assess for tumor progression/response. If multiple measurable lesions are present, up to 5 should be selected as “target” lesions. Target lesions should be selected on the basis of size and suitability for accurate repeated measurements. All other lesions will be followed as non-target lesions. The lower size limit of the target lesion(s) should be at least twice the thickness of the slices showing the tumor to decrease the partial volume effect (e.g., 8 mm lesion for a 4 mm slice).

Any change in size of non-target lesions should be noted, though does not need to be measured.

12.7.4 Response Criteria for Target Lesions

Response criteria are assessed based on the product of the longest diameter and its longest perpendicular diameter. Development of new disease or progression in any

established lesions is considered progressive disease, regardless of response in other lesions – e.g., when multiple lesions show opposite responses, the progressive disease takes precedence. Response Criteria for target lesions:

- **Complete Response (CR):** Disappearance of all target lesions. Off all steroids with stable or improving neurologic examination.
- **Partial response (PR):** $\geq 50\%$ decrease in the sum of the products of the two perpendicular diameters of all target lesions (up to 5), taking as reference the initial baseline measurements; on a stable or decreasing dose of steroids with a stable or improving neurologic examination.
- **Stable Disease (SD):** Neither sufficient decrease in the sum of the products of the two perpendicular diameters of all target lesions to qualify for PR, nor sufficient increase in a single target lesion to qualify for PD; on a stable or decreasing dose of steroids with a stable or improving neurologic examination.
- **Progressive Disease (PD):** 25% or more increase in the sum of the products of the perpendicular diameters of the target lesions, taking as reference the smallest sum of the products observed since the start of treatment, or the appearance of one or more new lesions.

Increasing doses of corticosteroids required to maintain stable neurological status should be strongly considered as a sign of clinical progression unless in the context of recent wean or transient neurologic change due e.g. to radiation effects.

12.7.5 Response Criteria for Non-Target Lesions:

- **Complete Response (CR):** Disappearance of all non-target lesions.
- **Incomplete Response/Stable Disease (IR/SD):** The persistence of one or more non-target lesions.
- **Progressive Disease (PD):** The appearance of one or more new lesions and/or unequivocal progression of existing non-target lesions.

12.7.6 Response criteria for tumor markers (if available):

Tumor markers will be classified simply as being at normal levels or at abnormally high levels.

12.7.7 Overall Response Assessment

The overall response assessment takes into account response in both target and non-target lesions, the appearance of new lesions and normalization of markers (where applicable), according to the criteria described in the table below. The overall response assessment is shown in the last column, and depends on the assessments of target, non-target, marker and new lesions in the preceding columns.

Target Lesions	Non-target Lesions	Markers	New Lesions	Overall
----------------	--------------------	---------	-------------	---------

				Response
CR	CR	Normal	No	CR
CR	IR/SD	Normal	No	PR
CR	CR, IR/SD	Abnormal	No	PR
PR	CR, IR/SD	Any	No	PR
SD	CR, IR/SD	Any	No	SD
PD	Any	Any	Yes or No	PD
Any	PD	Any	Yes or No	PD
Any	Any	Any	Yes	PD

Each patient will be classified according to his “best response” for the purposes of analysis of treatment effect. Best response is determined as outlined in [Section 12.9](#) from a sequence of overall response assessments.

12.8 Response Criteria for Patients with non- Hodgkin Lymphoma/Histiocytosis

Response and progression will be evaluated in this study using the new international criteria proposed by the revised Response Evaluation Criteria in Pediatric non-Hodgkin Lymphoma Criteria³¹, with modification from the Lugano classification.³²

12.8.1 Disease Parameters

12.8.1.1 Measurable disease:

A measurable node must have an LDi (longest diameter) greater than 1.5 cm. A measurable extranodal lesion should have an LDi greater than 1.0 cm. All tumor measurements must be recorded in millimeters (or decimal fractions of centimeters).

12.8.1.2 Non-measured disease:

All other lesions (including nodal, extranodal, and assessable disease) should be followed as nonmeasured disease (e.g., cutaneous, GI, bone, spleen, liver, kidneys, pleural or pericardial effusions, ascites).

12.8.1.3 Target lesions:

For patients staged with CT, up to six of the largest target nodes, nodal masses, or other lymphomatous lesions that are measurable in two diameters (longest diameter [LDi] and shortest diameter) should be identified from different body regions representative of the patient’s overall disease burden and include mediastinal and retroperitoneal disease, if involved.

12.8.2 Evaluation of Measurable Disease

Complete Response (CR)

Disappearance of all disease. CT or MRI should be free of residual mass or evidence of new disease. FDG-PET should be negative.

Complete Response Unconfirmed (CRu)

Residual mass is negative by FDG-PET; no new lesions by imaging examination; no new and/or progressive disease elsewhere

Partial Response (PR)

50% decrease in SPD (the sum of the products of the largest diameter and the perpendicular diameter for a tumor mass) on CT or MRI; FDG-PET may be positive (Deauville score of 4 or 5 with reduced lesional uptake compared with baseline); no new and/or PD; morphologic evidence of disease may be present in BM if present at diagnosis; however, there should be 50% reduction in percentage of lymphoma cells.

No Response (Stable Disease)

Neither sufficient shrinkage to qualify for PR nor sufficient increase to qualify for PD, taking as reference the smallest sum diameters while on study.

Progressive disease

For those with > 25% increase in SPD on CT or MRI, Deauville score 4 or 5 on FDG-PET with increase in lesional uptake from baseline, or development of new morphologic evidence of disease in BM

Evaluation of Non-measured Lesions (CT-based response, PET/CT based response not applicable)³²

Complete Response (CR): Absent non-measured lesions.

Partial response (PR): Absent/normal, regressed, lesions, but no increase.

Stable Disease (SD): No increase consistent with progression

Progressive Disease (PD): New or clear progression of preexisting non-measured lesions.

